12. SAFETY

12.1 Definition and Assessment of (Serious) Adverse Events and other safety related events

Adverse Event (AE) (Art. 2 Abs 57 MDR)

Any untoward medical occurrence, unintended disease or injury or any untoward clinical signs (including an abnormal laboratory finding) in subjects, users or other persons whether or not related to the medical device.

Serious Adverse Event (SAE) (Art. 2 Abs 58 MDR)

Any adverse event that led to any of the following:

- (a) death,
- (b) serious deterioration in the health of the subject that resulted in any of the following:
 - (i) life-threatening illness or injury,
 - (ii) permanent impairment of a body structure or a body function,
 - (iii) hospitalisation or prolongation of patient hospitalisation,
 - (iv) medical or surgical intervention to prevent life-threatening illness or injury or permanent impairment to a body structure or a body function,
 - (v) chronic disease,
- (c) foetal distress, foetal death or a congenital physical or mental impairment or birth defect.

Note: planned hospitalization for pre-existing condition, or a procedure required by the CIP, without a serious deterioration of the health status of the subject, is not considered an SAE

Device deficiency (Art. 2 Abs 59 MDR)

Inadequacy of a medical device related to its identity, quality, durability, reliability, safety or performance, of an investigational device, including malfunction, user errors and inadequate information supplied by the manufacturer. Device deficiency data will be collected by the blood banks and the clinic staff.

The blood bank teams will use the Hemanext ONE System to manufacture hypoxic RBCs. The Oslo blood bank will ship the hypoxic RBCs to the Bergen blood bank team for storage. Bergen blood bank team will confirm blood bag integrity prior to storage, when ordered for a subject and after each transfusion.

Malfunction (ISO14155)

Failure of an investigational device to perform in accordance with its intended purpose when used in accordance with the instructions for use or the CIP.

Device deficiency with Serious Adverse Device Effect (SADE) potential (Art. 80 Abs 1 letter c MDR; ISO14155)

Any device deficiency that might have led to a serious adverse event if appropriate action had not been taken, intervention had not occurred, or circumstances had been less fortunate.

Adverse Device Effect (ADE) (ISO14155)

Adverse event possibly, probably or causally related to the use of an investigational device or procedures.

Serious Adverse Device Effect (SADE) (ISO14155)

Adverse device effect (ADE) that has resulted in any of the consequences characteristic of a serious adverse event.

Unanticipated Serious Adverse Device Effect (USADE) (ISO14155)

Serious adverse device effect (SADE) which by its nature, incidence, severity or outcome has not been identified in the current version of the risk analysis report.

Causal Relationship of SAE (MDCG 2020-10/1)

A causal relationship towards the medical device or the procedure of the investigation should be rated by the PI and the Sponsor as follows:

- Not related: The relationship to the device or procedures can be excluded.
- **Possible:** The relationship with the use of the investigational device is weak but cannot be ruled out completely. Alternative causes are also possible.
- **Probable:** The relationship with the use of the investigational device seems relevant and/or the event cannot reasonably be explained by another cause.
- **Causal relationship:** The serious event is associated with the investigational device or with procedures beyond reasonable doubt.

Investigational Medical Device:

A device that is assessed in a clinical investigation. Note: An investigational device can be a non-CE marked device or a CE marked device. The definition is understood to cover also the devices investigated in post-market surveillance investigations.

Case Report Form (CRF): A printed, optical, or electronic document designed to record all of the protocol required information to be reported to the sponsor on each trial subject.

Serious Health Threat:

signal from any adverse event or device deficiency that indicates an imminent risk of death or a serious deterioration in the health in subjects, users or other persons, and that requires prompt remedial action for other subjects, users or other persons

Note: This would include events that are of significant and unexpected nature such that they become alarming as a potential serious health hazard or possibility of multiple deaths occurring at short intervals.

Unanticipated / Unexpected Serious Adverse Device Effect (USADE)

- According to ISO 14155:2020: Serious adverse device effect which by its nature, incidence, severity or outcome has not been identified in the current risk assessment.

12.2 Documentation and reporting in Medical Device clinical investigations

Device deficiencies and all **adverse events (AE)** including all **serious adverse events (SAE)** are collected, fully investigated and documented in the source document and appropriate CRF during the entire investigation period, i.e. from patient's informed consent until the last CIP-specific procedure, including a safety follow-up period.

- Documentation of AEs (including SAEs) by the PI includes diagnosis or symptoms, start and stop dates of event, event treatment, event resolution, assessment of seriousness and causal relationship to MD and/or investigation procedure (ISO14155).
- Documentation of DDs by the PI includes description of event, start date, investigational device information, action taken with regard to the investigational device, and whether the DD led to an AE. The Sponsor shall review all DDs and determine and document in writing whether they could have led to a SAE (DD with SADE potential) (ISO14155).

The Sponsor provides the CEC with the documentation at their request

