10.1.1 Experimental Intervention (medical device)

Units of hypoxic RBCs will be manufactured at Oslo's University Blood Bank or Haukeland University Hospital's Blood Bank using Hemanext ONE system. The hypoxic RBCs manufactured in Oslo will be shipped to the Blood Bank at Haukeland University Hospital where they will be stored at 1-6°C for up to 42 days. Participants who would normally receive a transfusion of units of conventional RBCs will instead receive a transfusion of 2 units of hypoxic RBCs and any additional conventional RBCs as needed. All transfusions will be performed according to the site's SOPs.

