12.4 Reporting of (Serious) Adverse Events, device deficiencies, and other safety related events

12.4.1 Reporting to the Sponsor:

The following events are to be reported to the Sponsor by the PI (or authorized designee) within 24 hours after becoming aware of the event:

- All SAEs
- Health hazards that require measures
- Device deficiencies

The Sponsor will evaluate SAEs with regard to causality and seriousness. Device deficiencies are also assessed regarding their potential to lead to an SAE (DD with SADE potential).

12.4.2 Reporting to the Competent Ethics Committee:

The following events are to be reported to the CEC promptly:

- a. any serious adverse event which has a causal relation with the MD, comparator or procedure/test method or where a causal relation appears to be possible (SADE);
- b. any device deficiency which, in the absence of appropriate measures or intervention or in less favourable circumstances, could have led to serious adverse events (DD with SADE potential);
- c. any new information relating to an event already notified under points (a) and (b).

In order to ensure prompt notification, the Sponsor may initially submit an incomplete notification.

If safety and health hazards that require measures must be taken immediately during the conduct of the investigation, the Sponsor notifies the CEC within 2 days of these measures and the circumstances which made them necessary.

Periodic safety reporting:

An Annual Safety Report (ASR) is submitted by the Sponsor to the CEC, yearly. The ASR contains a list of all SADEs and DDs and a report on their degree of seriousness, causal relationship with the MD and procedure and on subjects' safety.

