12.7 Reporting of Safety related events

Reporting to the Sponsor:

All SAEs, device deficiencies and health hazards that require measures are reported to the Sponsor by the PI (or authorized designee) within 24 hours after becoming aware of the event. Device deficiencies are assessed regarding their potential to lead to an SAE. DD are assessed regarding their potential to lead to an SAE.

12.7.1 Reporting to the Competent Ethics Committee:

The Sponsor reports to the CEC promptly any serious adverse event which has a causal relation with the MD, comparator or procedure/test method or where a causal relation appears to be possible.

In order to ensure prompt notification, the Sponsor may initially submit an incomplete notification.

If safety and health hazards that require measures must be taken immediately during the conduct of the investigation, the Sponsor notifies the CEC within 2 days of these measures and the circumstances which made them necessary.

12.7.2 Periodic safety reporting:

An Annual Safety Report (ASR) is submitted by the Sponsor to the CEC, yearly. The ASR contains a list of all SADEs and DDs and a report on their degree of seriousness, causal relationship with the MD and procedure and on subjects' safety.

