7.8.2 Adverse Device Effect

An overview of all adverse device effects for both patient groups will be presented, including the number and percentage of patient s with at least one, and the total number, of the following:

- Adverse Device Effect (ADE) overall up to 7 days (+/- 1 day) after the transfusion.
- Adverse Device Effect (ADE) (all types/grades) within a time frame up to 24 hours following the transfusion.
- Serious Adverse Device Event (SAE)
- Any adverse device event from enrolment up to 7 days (+/- 1 day) following the transfusion
- Any adverse device event overall

LINK Medical Study ID: HEM001

- Device Deficiency
- Malfunction of Device
- Action taken because of the Adverse Device Effect
- Medication or treatment given because of the Adverse Device Effect
- Adverse Device Effect broken down by Severity.
- Serious Adverse Device Effect broken down by Anticipation
- Adverse Device Effect broken down by Relationship to medical device.
- Adverse Device Effect broken down by Relationship study procedure.
- Adverse Device Effect broken down by Seriousness.

The incidence of adverse device events will be presented by system organ class and preferred term. For each system organ class and preferred term, the total number of adverse events as well as the number and percentage of patient s with at least one adverse event in that system organ class or preferred term will be presented.

7.8.3 The decision regarding the classification of Unanticipated/Anticipated Adverse Device Effects will be made during the clean file meeting.Hemoglobin Evaluation

Summary statistics on the Hemoglobin test result will be presented by visit and by time point. For postbaseline visits, summary statistics on the change from baseline will also be presented. A frequency table on the clinical interpretation of Hemoglobin test results (*e.g.*, normal, abnormal but not clinically significant, abnormal and clinically significant) will be presented by visit. For the post transfusion evaluation, the shift from baseline will also be presented.

Summary statistic on the Hemoglobin level before the following transfusion will also be presented, defined as the Hemoglobin assessment conducted immediately prior to the upcoming transfusion or the Hemoglobin assessment at Visit 5.

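### The device-deficiency window opens at patient consent, which conflicts with collection at the blood banks, and the SAP percentage cannot count a unit that fails before issue

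*Protocol*

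**What the plan says.** Protocol 12.2 says that device deficiencies, like adverse events, are collected and recorded in the source document and CRF "during the entire investigation period, i.e. from patient's informed consent until the last CIP-specific procedure, including a safety follow-up period". Section 12.6 repeats this. The recorder is the PI: "Documentation of DDs by the PI includes description of event, start date, investigational device information". Section 12.1 defines the CRF as a record for each trial subject.

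Section 12.1 also assigns the task more widely: "Device deficiency data will be collected by the blood banks and the clinic staff". SAP 6.1.7 says the same. Section 12.1 adds that the "Bergen blood bank team will confirm blood bag integrity prior to storage, when ordered for a subject and after each transfusion". Under 10.1.1, units made in Oslo "will be shipped to the Blood Bank at Haukeland University Hospital where they will be stored at 1-6°C for up to 42 days".

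On reporting, 12.7 states that SAEs, device deficiencies and health hazards "are reported to the Sponsor by the PI (or authorized designee) within 24 hours after becoming aware of the event"; 12.4.1 agrees. Section 12.8.1 allows up to 3 calendar days for reportable events. Under 12.8.2 these include deficiencies that could have led to an SAE.

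SAP 7.8.2 lists Device Deficiency and Malfunction in an overview "including the number and percentage of patient s with at least one, and the total number, of the following". SAP 7.1.1 makes patients in the applicable analysis set the default denominator.

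**The concern.** Hemanext ONE is a processing and storage kit. Oxygen reduction, transfer to the storage bag, any shipment from Oslo and cold storage all take place before a unit is issued. A window that opens at a patient's consent and a record kept per subject do not suit failures at those steps. A kit that leaks during processing, or a unit rejected at the pre-storage check, has no recipient, no consent date and no CRF.

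The protocol itself treats such failures as important. Section 12.9 names an undetected leak in the storage bag, with loss of sterility, as a device risk, along with sickle-trait testing failures and a non-indicated additive solution. Leaks caught before issue are the natural warning sign for those that are not caught. Section 12.8.2 makes a deficiency reportable if harm was avoided only because someone acted, which can describe a leak found at inspection. If such events do not reach the study database, the deficiency table describes mainly units that had already passed inspection.

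**Working it through.** The plan states no deficiency rate, so there is no figure of its own to reproduce. The check sets the texts side by side and then illustrates the denominator.

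**Who collects, and when**
- Protocol 12.1 and SAP 6.1.7: blood banks and clinic staff collect. Bergen checks bags before storage, on order and after transfusion. No consent condition is stated.
- Protocol 12.2 and 12.6: the PI documents in the source document and CRF, from the patient's consent.
- Protocol 11.1.1 and 11.1.2, SAP Appendices A and B: device integrity review is scheduled only at Visit 2. Sections 11.3.3 to 11.3.5 list deficiencies only at patient visits.

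The pre-storage check is thus required by one section and can lie outside the collection window of two others.

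**How often processing precedes the recipient's consent**
- Inputs: consent on D0 and transfusion on D1 (flow charts); storage up to 42 days (10.1.1, 10.1.4).
- A unit more than about 1 day old at transfusion was processed before its recipient consented.
- Assumption: unit age is uniform from 0 to A days. The documents give only the maximum. Share = (A − 1)/A.

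| A (days) | Share processed before consent |
|---|---|
| 7 | 6/7 = 85.7% |
| 14 | 13/14 = 92.9% |
| 28 | 27/28 = 96.4% |
| 42 | 41/42 = 97.6% |

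If consent is read at study level instead (the first patient's consent), only units processed before that date are outside the window.

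**What the SAP table can show**
- Inputs: 20 patients (SAP 5.1) and 2 hypoxic units each (10.1.1). 20 × 2 = 40 transfused units. This is a minimum, because 10.1 says at least two.
- Assumption: w further kits fail before issue and the 40 transfused units are sound. Per-kit rate = w/(40 + w).

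| w (assumed) | Per kit | Percentage of patients |
|---|---|---|
| 1 | 1/41 = 2.4% | 0/20 = 0% |
| 2 | 2/42 = 4.8% | 0/20 = 0% |
| 4 | 4/44 = 9.1% | 0/20 = 0% |

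The patient percentage stays at zero whatever w is. The total number would be w if these events reach the database and 0 if they do not, and neither document says which. Even for issued units the two scales differ: one deficient transfused unit is 1/20 = 5.0% of patients and 1/40 = 2.5% of units.

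**The case against.** A reader might infer that failures before issue are excluded by design, or that the trial would report no deficiencies although kits had failed. The documents do not support either reading.
- Blood banks are told to collect deficiency data (12.1, SAP 6.1.7).
- Section 10.7 requires every kit to be accounted for in a log, and 10.8 sends deficient devices back to the sponsor. Neither mentions consent.
- Reporting may be done by an authorized designee (12.4.1, 12.7), who could be blood-bank staff. The administrative pages before Protocol 3.4 are not in the text available, so a named blood-bank role there cannot be ruled out.
- The Annual Safety Report lists all deficiencies (12.4.2, 12.7.2).
- SAP 7.8.2 gives a total number beside the patient percentage, so an unlinked deficiency could be counted there.

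It can also be said that the objectives concern transfused patients, that no outcome measures kit performance, and that patient-level tables suit a descriptive safety study.

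Most of this stands. The sponsor has routes by which it could learn of a failure before issue. What is missing is the link from those routes to the study data: no rule says how a deficiency without a patient enters the CRF, the database or the SAP total, and the window as worded points the other way. The patient-level focus explains the AE tables, but SAP 7.8.2 does choose to report Device Deficiency and Malfunction, and for a processing kit the patient is the wrong unit for that percentage.

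**Conclusion.** The point holds as an internal contradiction and a mismatched denominator. Protocol 12.1 and SAP 6.1.7 cannot be fully applied together with the consent-based window in 12.2 and 12.6. A unit never issued cannot enter the SAP percentage, and nothing written brings it into the total. The table may therefore understate deficiencies.

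The size of any understatement is unknown. The discard counts and the unit-age distribution above are assumptions, and 40 units assumes exactly two for each of 20 patients. The shares processed before consent apply only if consent is read per recipient. Under the study-level reading the window problem shrinks to units made before the first consent, but the denominator problem is unchanged. The primary outcome, a count of patients with adverse events, is not affected by units that reach no patient.

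**What to change.** 1. **Protocol 12.2 and 12.6.** Start the device-deficiency window at kit receipt or first use at either blood bank and run it to final disposition, independent of patient consent. This brings both sections into line with 12.1 and SAP 6.1.7. Leave the adverse-event window as it is.
2. **Protocol 12.4.1 and 12.7.** Name the Oslo and Bergen blood banks as authorized designees for reporting deficiencies to the sponsor. Reconcile the 24-hour limit there with the 3-calendar-day limit in 12.8.1, since a deficiency that could have led to an SAE falls under both.
3. **SAP 7.8.2.** Add counts of Device Deficiency and Malfunction per kit processed, split into before and after issue. Keep the patient-level percentage for issued units only.

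The per-kit counts need two sources. The log in 10.7 follows a kit only until it is used for processing, destroyed or returned, so a unit that later leaks in storage may appear there simply as used. The blood banks' own unit-tracking records, also mentioned in 10.7, must supply the rest.

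The cost is protocol and SAP wording, some reconciliation of blood-bank records, and a deficiency rate that may look less favourable. No patient procedure is added.

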12.3 Foreseeable adverse events and anticipated adverse device effects

There were no adverse device effects associated with the Hemanext RBC Processing System reported in the earlier in vivo pivotal human trial (cf. Investigator Brochure).

Well established blood transfusion complications (acute and delayed transfusion related effects) known to occur in medical practice using a conventional method of blood processing and storage will be considered as expected events. These effects are listed below³⁸:

- Transfusion-associated graft versus host disease
- Transfusion-related acute lung injury (TRALI)
- Post transfusion purpura
- Transfusion-associated circulatory overload (TACO)
- Transfusion-transmitted infection (TTI)
- Allergic reaction
- Transfusion-associated dyspnea (TAD)
- Febrile non-hemolytic transfusion reaction (FNHTR)
- Hypotensive transfusion reaction
- Delayed hemolytic transfusion reaction (DHTR)
- Delayed serologic transfusion reaction (DSTR)
- Acute hemolytic transfusion reaction (AHTR)
- Major cardiac event (MCE)
- Haematoma (bruise)
- Arterial puncture
- Delayed bleeding (re-bleeding)
- Nerve injury/irritation
- Localized infection/inflammation
- Deep venous thrombosis (DVT)
- Arteriovenous fistula
- Compartment syndrome
- Brachial artery pseudo-aneurysm

12.4 Reporting of (Serious) Adverse Events, device deficiencies, and other safety related events

12.4.1 Reporting to the Sponsor:

The following events are to be reported to the Sponsor by the PI (or authorized designee) within 24 hours after becoming aware of the event:

- All SAEs
- Health hazards that require measures
- Device deficiencies

The Sponsor will evaluate SAEs with regard to causality and seriousness. Device deficiencies are also assessed regarding their potential to lead to an SAE (DD with SADE potential).

12.4.2 Reporting to the Competent Ethics Committee:

The following events are to be reported to the CEC promptly:

- a. any serious adverse event which has a causal relation with the MD, comparator or procedure/test method or where a causal relation appears to be possible (SADE);
- b. any device deficiency which, in the absence of appropriate measures or intervention or in less favourable circumstances, could have led to serious adverse events (DD with SADE potential);
- c. any new information relating to an event already notified under points (a) and (b).

In order to ensure prompt notification, the Sponsor may initially submit an incomplete notification.

If safety and health hazards that require measures must be taken immediately during the conduct of the investigation, the Sponsor notifies the CEC within 2 days of these measures and the circumstances which made them necessary.

Periodic safety reporting:

An Annual Safety Report (ASR) is submitted by the Sponsor to the CEC, yearly. The ASR contains a list of all SADEs and DDs and a report on their degree of seriousness, causal relationship with the MD and procedure and on subjects' safety.

12.5 Follow-up of (Serious) Adverse Events

For serious adverse device event, and serious procedure related event the immediate report will be followed by detailed, written follow-up reports (using the SAE notification form found in the study site binder). Both the immediate and follow-up reports will identify subjects by unique code numbers assigned to the latter.

12.6 Documentation and reporting in Medical Device clinical investigations

Device deficiencies (DD) and all **adverse events (AE)** including all **serious adverse events (SAE)** are collected, fully investigated and documented in the source document and appropriate case report form (CRF) during the entire investigation period, i.e. from patient's informed consent until the last CIP-specific procedure, including a safety follow-up period.

- Documentation of AEs (including SAEs) by the PI includes diagnosis or symptoms, start and stop dates of event, event treatment, event resolution, assessment of seriousness and causal relationship to MD and/or investigation procedure (ISO14155).
- Documentation of DDs by the PI includes description of event, start date, investigational device information, action taken with regard to the investigational device, and whether the DD led to an AE. The Sponsor shall review all DDs and determine and document in writing whether they could have led to a SAE (DD with SADE potential) (ISO14155).

There were no adverse device effects associated with the Hemanext RBC Processing System reported in the earlier in vivo pivotal human trial (see Investigator Brochure).

Well established blood transfusion complications (acute and delayed transfusion related effects) known to occur in medical practice using a conventional method of blood processing and storage will be considered as expected events. These effects are listed below³⁸:

- Transfusion-associated graft versus host disease
- Transfusion-related acute lung injury (TRALI)
- Post transfusion purpura
- Transfusion-associated circulatory overload (TACO)
- Transfusion-transmitted infection (TTI)
- Allergic reaction
- Transfusion-associated dyspnea (TAD)
- Febrile non-hemolytic transfusion reaction (FNHTR)
- Hypotensive transfusion reaction
- Delayed hemolytic transfusion reaction (DHTR)
- Delayed serologic transfusion reaction (DSTR)
- Acute hemolytic transfusion reaction (AHTR)
- Major cardiac event (MCE)
- Haematoma (bruise)
- Arterial puncture
- Delayed bleeding (re-bleeding)
- Nerve injury/irritation
- Localized infection/inflammation

- Deep venous thrombosis (DVT)
- Arteriovenous fistula
- Compartment syndrome
- Brachial artery pseudo-aneurysm
- Vasovagal reactions

